The treatment groups are as follows:

Group A: 21mg nicotine patch + lorcaserin 10mg twice daily for the 14 week study period followed by a 2 week taper of the nicotine patch (14mg for 1 week; 7mg for 1 week).

Group B: 21mg nicotine patch + placebo for the first 2 weeks; 21mg nicotine patch + lorcaserin 10mg twice daily for the next 12 weeks followed by a 2 week taper of the nicotine patch (14mg for 1 week; 7mg for 1 week).

The Study timeline is shown below:

Blinding

In order to maintain a double-blind assignment to treatment conditions, subjects receiving nicotine patch alone (Group B) will receive placebo lorcaserin tablets during the first two weeks.

Screening and Session Procedures

Interested potential subjects will respond to advertisements by contacting our Center to be phone screened. Potential subjects will be given a brief description of the study and will be asked questions to assess eligibility and interest. Eligible subjects interested in participating will be scheduled for the medical history and physical examination screening visit.

After granting their informed consent, potential subjects will be given the HIPAA Notice of Privacy Practices. They will also complete a medical history form and will have their blood pressure, pulse, weight, height, temperature and expired air CO measured.

Subjects will provide smoking history information, a saliva sample, blood (maximum of 20mL) for tests to measure general health, and urine for urinalysis and illicit drug testing. Women of child bearing potential will also have a serum pregnancy test. The study physician or one of his assistants will perform a physical examination and an ECG. The

initial target Quit Day for all the subjects will be established at screening. The screening visit will last approximately 2 hours.

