Blood and urine specimens will be sent to LabCorp for processing. The results of laboratory blood and urine tests will not routinely be given to participants to send or be sent to their physician to include in their medical record. However, if the subject's lab results are outside the acceptable range for participation in the study the Physician/P.A. will send the subject a medical exclusion letter and a copy of the lab results. Participants who are accepted into the study but need medical follow up due to minor abnormalities in lab results will also be informed by letter from the Physician/P.A. A copy of the laboratory results will be included with the letter, which will also indicate that the condition does not interfere with his/her participation in the study.

The time commitment for subjects is 16 weeks: 4 weeks of pre-cessation treatment before the scheduled Quit Day and 12 weeks of additional post-Quit Day treatment, plus one follow-up session at six months (if eligible) after the Quit Day.

Questionnaires will be completed within REDCap on a desktop computer in the Center office. The technician will log on to the REDCap site and will open the questionnaires for the subjects. Subjects will only have access to their questionnaires. Access to any other websites will be blocked by Psychiatry Information Technology.

Session P1

The first study visit will take place approximately one week after the screening visit. Subjects will complete baseline questionnaires and will be randomized to either Group A (nicotine patch + lorcaserin) or Group B (nicotine patch + placebo). Subjects will be tested for exhaled air carbon monoxide and smoking related chemicals in the saliva. They will also have their blood pressure, heart rate and weight measured. Females of child bearing potential will also complete a urine pregnancy test which must be negative in order to continue study participation. Subjects will also complete questionnaires rating craving, withdrawal symptoms, side effects, and sensory experience.

Subjects will be given a supply of study medications (depending on randomization) to use for 2 weeks and will receive verbal and written instructions on how to take them.

Subjects will also be given diaries to record medication use and the number of cigarettes smoked each day and will be instructed to return the diaries at the next visit. They will also be asked to return any unused medications for proper disposal and compliance monitoring.

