Subjects will be called within three days after the first day of treatment to make sure that medications are being used as directed.

Session P2

The second study visit will take place 2 weeks after the first visit. Subjects will be tested for exhaled air carbon monoxide and smoking related chemicals in the saliva. Subjects

will also have their blood pressure, heart rate and weight measured. In addition, they will also complete questionnaires rating craving, withdrawal symptoms, side effects, and sensory experience.

A laboratory session will be conducted at this visit. Participants will be asked to refrain from smoking after midnight the night before the session. After an additional 2 hour period in which subjects refrain from smoking, withdrawal symptoms will be assessed as well the ability to delay smoking in a simulated smoking lapse paradigm validated by McKee et al (2012). In this paradigm smokers are allowed to smoke but are offered a monetary incentive to delay smoking, which decreases over time in the session.

Subjects in both Group A and Group B will be given a supply of study medications (nicotine patch + lorcaserin). Following the P2 laboratory session, the group that received nicotine patch + placebo will be switched to receiving nicotine patch+ lorcaserin, and the nicotine patch+ lorcaserin group will continue receiving nicotine patch+ lorcaserin, for an additional 2 weeks leading up to a scheduled target quit-smoking date (TQD).

Subjects will also be given diaries to record medication use and the number of cigarettes smoked each day and will be instructed to return the diaries at the next visit. They will also be asked to return any unused medications for proper disposal and compliance monitoring.

Session P3 (the day before Quit Day)

The third study visit will take place 2 weeks after the second visit (and one day prior to the Quit Day). Subjects will be tested for exhaled air carbon monoxide and smoking related chemicals in the saliva. Subjects will also have their blood pressure, heart rate and weight measured. Females of child bearing potential will also complete a urine pregnancy test which must be negative in order to continue study participation. They will also complete questionnaires rating craving, withdrawal symptoms, side effects, and sensory experience.

Subjects will be dispensed a sufficient supply of nicotine patches and lorcaserin to last until the next scheduled visit.

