Subjects will also be given diaries to record medication use and the number of cigarettes smoked each day and will be instructed to return the diaries at the next visit. They will also be asked to return any unused medications for proper disposal and compliance monitoring. In addition, they will be given forms to be completed on their Quit Day. They will be asked to return these forms at their next visit.

Sessions C1-C4

Session C1 will take place 1 week after Session P3. Session C2 will take place 2 weeks after C1. Session C3 will occur 3 weeks after C2, and Session C4 will occur 4 weeks after C3.

Subjects will be tested for exhaled air carbon monoxide and smoking related chemicals in the saliva. Subjects will also have their blood pressure, heart rate and weight measured. In addition, they will also complete questionnaires rating craving, withdrawal symptoms, side effects, and sensory experience.

At Sessions C2 and C3 females of child bearing potential will complete a urine pregnancy test which must be negative in order to continue study participation.

At Sessions C1-C3 subjects will be dispensed a sufficient supply of nicotine patches and lorcaserin to last until the next scheduled visit. At session C4 subjects will be given instructions for tapering off of the patch. They will be given a 1 week supply of 14mg nicotine patches and a 1 week supply of 7 mg nicotine patches. A technician will call them 2 weeks after the C4 session to follow up on the patch tapering process.

Subjects will also be given diaries to record medication use and the number of cigarettes smoked each day and will be instructed to return the diaries at the next visit. They will also be asked to return any unused medications for proper disposal and compliance monitoring.

Six-month Follow-up

Study participants will be contacted by phone, letter or email six months after their Quit Day and asked about their current smoking behavior, as well as their smoking behavior since their last session. Those subjects who report continuous or point abstinence (no smoking in the previous seven days) and have not used any smoking cessation aid will be asked to return to the laboratory for a brief follow-up session. This session will include an expired air CO reading; blood pressure, heart rate and weight measurements; collection of a saliva sample; and completion of several questionnaires.

SUBJECT IDENTIFICATION:

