- Coronary heart disease with symptoms (e.g., chest pain, shortness of breath);
- Heart attack in the past year;
- Cardiac rhythm disorder (irregular heart rhythm);
- Chest pain in the last month (unless history, exam, and ECG clearly indicate a non-cardiac source);
- Symptomatic cardiac (heart) disorder (including but not limited to valvular heart disease, heart murmur, heart failure);
- Liver disease or kidney disorder that requires medication or a change in diet or lifestyle;
- Major gastrointestinal illness (e.g. Celiac disease, Crohn's dx Ulcerative Colitis) that require medication;
- Active ulcers in the past 30 days;
- Currently symptomatic lung disorder/disease that requires oxygen;
- Major brain disorder (including but not limited to stroke with residual deficit, brain tumor, and seizure disorder);
- Migraine headaches that occur more frequently than once per week;
- Recent, unexplained fainting spells;

- Problems giving blood samples;
- Diabetes (unless controlled by diet and exercise alone and screening glucose is less than 180mg/dl and HbA1c is less than 7%);
- Current cancer or treatment for cancer in the past six months (except basal or squamous cell skin cancer);
- HIV, Hepatitis B, or Hepatitis C
- History of Tuberculosis or recent positive PPD
- Other major medical condition;
- Current symptomatic psychiatric disease (with the exception of anxiety disorders, OCD and ADHD);
- Psychosis, bipolar disorder, or psychiatric hospitalization within the past 12 months;
- Suicidal ideating (thinking about ways to commit suicide) (within the past 10 years) or lifetime occurrence of attempted suicide;
- Current depression - The Patient Health Questionnaire PHQ-9 for Depression will be used to screen for current (within 2 weeks) depression. Potential subjects who score >9 (or who score >0 on item #9 ("Thoughts that you would be better off dead, or of hurting yourself in some way")) will be excluded from study participation, and, at the discretion of the study physician, referred to appropriate psychiatric treatment;
- Bulimia or anorexia;
- Pregnant or nursing mothers
- BMI of < 18.5 kg/m² or > 38 kg/m²;
- Prior use of fenfluramine or dexfenfluramine
- Use (within the past 30 days) of:

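### The pregnancy-test calendar does not line up with drug exposure at two points: Group B's first lorcaserin after P2, and the six weeks of treatment after the last test at C3

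*Combined protocol and SAP*

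**What the plan says.** All references are to the combined protocol and SAP.

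- **Exclusion Criteria** list "Pregnant or nursing mothers". **Inclusion Criteria** require acceptable contraception throughout participation and name the accepted methods.
- **Screening and Session Procedures**: "Women of child bearing potential will also have a serum pregnancy test".
- **Session P1**: "Females of child bearing potential will also complete a urine pregnancy test which must be negative in order to continue study participation". The same condition is stated under **Session P3**.
- **Session P2** lists CO, saliva, blood pressure, heart rate, weight, questionnaires and the laboratory session, but no pregnancy test. After the laboratory session "the group that received nicotine patch + placebo will be switched to receiving nicotine patch+ lorcaserin".
- **Sessions C1-C4**: "At Sessions C2 and C3 females of child bearing potential will complete a urine pregnancy test which must be negative". No test is listed at C1 or C4. Lorcaserin and patches are dispensed at C1 to C3 to last until the next visit. At C4 only taper patches are dispensed: "They will be given a 1 week supply of 14mg nicotine patches", plus one week of 7 mg patches.
- **After C4** there is a telephone call about the taper and a six-month contact. The in-person six-month visit is limited to participants who report abstinence without a cessation aid, and it lists no pregnancy test.

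**The concern.** Repeated testing on top of screening and contraception shows that the protocol does not rely on those two safeguards alone. One would then expect the tests to follow exposure, or a reason why they do not. The calendar fits Group A's lorcaserin start but not Group B's, and it stops while both drugs are still being taken.

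What is at stake is participant safety. A pregnancy that becomes detectable between P1 and P2 would not be picked up by a scheduled test before Group B's first lorcaserin dose. One beginning after C3 would not be picked up by any scheduled test, and taper patches would be handed out at C4 without the condition applied at the four test visits.

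There is a smaller point at P1. That section mentions randomisation before it mentions the test and does not say which comes first. A positive result after randomisation would be a post-randomisation loss and not a screen failure. The Data Analysis section has no rule for randomised participants who do not continue.

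**Working it through.** **Inputs.** Visit intervals come from Sessions P1, P2, P3 and C1-C4. P1 is set to week 0: "The first study visit will take place approximately one week after the screening visit", and "The second study visit will take place 2 weeks after the first visit". Later intervals are 2 weeks (P2 to P3), 1 (P3 to C1), 2 (C1 to C2), 3 (C2 to C3), 4 (C3 to C4) and 2 (taper).

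**Step 1: reproduce the plan's timeline.** Each visit week is the previous visit week plus the stated interval.

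| Visit | Week | Urine test listed | Treatment event |
|---|---|---|---|
| P1 | 0 | yes | Group A starts lorcaserin; both groups start patches |
| P2 | 0 + 2 = 2 | no | Group B starts lorcaserin |
| P3 | 2 + 2 = 4 | yes | both drugs dispensed |
| C1 | 4 + 1 = 5 | no | both drugs dispensed |
| C2 | 5 + 2 = 7 | yes | both drugs dispensed |
| C3 | 7 + 3 = 10 | yes | last lorcaserin dispensed |
| C4 | 10 + 4 = 14 | no | lorcaserin ends; taper patches dispensed |
| End of taper | 14 + 2 = 16 | no | patches end |

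The plan states 4 weeks before and 12 weeks after the Quit Day: 4 + 12 = 16. The timeline is reproduced.

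**Step 2: last test to first lorcaserin.**
- Group A: 0 − 0 = 0 weeks.
- Group B: 2 − 0 = 2 weeks.

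**Step 3: intervals between tests, and time after the last one.**
- Between tests: 4 − 0 = 4, 7 − 4 = 3 and 10 − 7 = 3 weeks.
- Last test to end of lorcaserin: 14 − 10 = 4 weeks.
- Last test to end of patches: 16 − 10 = 6 weeks.

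The 4 weeks of lorcaserin after C3 equal the P1-to-P3 interval, but that interval is closed by a test and this one is not. The full 6 weeks exceed every interval between tests.

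**Step 4: share of treatment days after the last test.**
- Lorcaserin, Group A: 28 / 98 = 28.6%.
- Lorcaserin, Group B: 28 / 84 = 33.3%.
- Patches, both groups: 42 / 112 = 37.5%.

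These are shares of calendar time, not of risk. The documents do not give the number of women of child-bearing potential, so no expected count of pregnancies can be derived.

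**Step 5: what P2 and C4 would change, as arithmetic only.** With tests also at weeks 2 and 14, the time from last test to first lorcaserin would be 0 weeks in both groups, and 16 − 14 = 2 weeks of patches would follow the last test. No lorcaserin is dispensed at C4, so a test there could reveal exposure in the preceding 4 weeks but not prevent it. It could precede only the last 14 patch days.

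**Step 6: effect on the primary analysis.** Time-to-lapse is measured in the P2 laboratory session, before Group B switches. Neither gap affects that measurement or the power stated for it.

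**The case against.** The strongest reply is that the protocol breaks no rule of its own. Nowhere does it say that a test accompanies every dispensing visit or every first dose, and C1 also dispenses lorcaserin without one. Group B reaches P2 after a serum test and a urine test, under a contraception requirement, with its last test only 2 weeks old; every later interval between tests is longer. All of this stands. It makes the point a gap to be explained and not a contradiction, and it limits its weight. It does not explain why the first lorcaserin dose comes with a test in one group and not in the other, or why the longest untested stretch falls at the end. C1 is a weaker case: it comes one week after the P3 test and is not a first exposure.

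Some stronger readings are tempting, and the documents do not support them:

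- *The arms have different safeguards.* Both follow one visit and test calendar and the same contraception rule, and both start patches with a same-visit test. The only difference is when Group B's lorcaserin starts.
- *Late pregnancies are never detected.* Side-effect questionnaires, the taper call, the six-month contact and 24-hour contact numbers leave room for self-report. The consent pages, which might cover pregnancy reporting, are not in the text supplied, so its absence cannot be inferred.
- *The Aim 4 weight result would be distorted.* Nothing in the documents gives such an effect a size, and that analysis covers only abstinent participants.
- *Randomisation precedes the P1 test.* This rests on sentence order in a list of visit activities. The order is unstated, which is a reason to state it and not evidence of an error.

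**Conclusion.** The point holds as a specific, low-cost participant-safety gap. Group B's first lorcaserin comes 2 weeks after its last scheduled pregnancy test, against 0 weeks in Group A. After the last test at C3, 4 weeks of lorcaserin plus patch and a further 2 weeks of taper patches follow with no scheduled test. A pregnancy beginning after C3 would come to light only by self-report or other unscheduled means.

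This assumes that visits take place at the stated intervals and that the procedures listed for each visit are complete. It is not an arithmetic error, it breaks no stated rule, and the primary endpoint and power are unaffected.

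**What to change.** The sponsor should reconcile the pregnancy-test schedule with the dispensing schedule across Sessions P1 to C4 at two visits: P2, for Group B's first lorcaserin, and C4, for the end of lorcaserin and the taper patches. This can be done by bringing these visits under the existing condition or by stating why they are exempt; that clinical decision is the sponsor's. The Session P1 text should also make clear that the test result is known before randomisation.

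The cost is protocol wording and, if tests are added, at most two extra urine strips per woman of child-bearing potential. With 60 randomised, the ceiling is 2 × 60 = 120 strips even if every participant were such a woman. The visits are already attended and the test is already in use.

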Because of the nature of this study and the amount of questionnaires that subjects are expected to complete, we do not recruit potential subjects who do not read, are blind or who do not read/understand English. We are not equipped to validate alternate versions of our questionnaires, most of which are not published. Questionnaires cannot be administered orally by a translator or by Technicians to illiterate or blind subjects because the data obtained would not be comparable to self-administered questionnaires.

RISK/BENEFIT ASSESSMENT

Continuing to smoke carries significant health risks. Subjects enrolling in this study are attempting to quit smoking, and will receive two FDA-approved medications. The nicotine patch is approved for smoking cessation. Lorcaserin is approved for weight loss. A Phase II study conducted by Shanahan et al (2015) recently showed that lorcaserin is efficacious for smoking cessation. To date, hundreds of thousands of individuals have used lorcaserin with no major adverse events (death, permanent injury, hospitalization) reported (personal communication with [name], former CEO of Arena Pharmaceuticals). With smoking prevalence in society of 18.3% (higher in prior years) (CDC 2014) it is estimated of these it is reasonable to assume that a substantial proportion of individuals using lorcaserin has used the medication in combination with nicotine provided through tobacco use. Because of this, we do not anticipate adverse drug interactions with the combination of lorcaserin and nicotine provided via patch.

Potential side effects of Nicotine patch: Insomnia and abnormal dreams are common and expected side effects associated with 24-hour nicotine patches. If a subject complains of disturbed sleep, he or she will be instructed to remove the patch at bedtime and apply a new one the next day at the usual time. Skin irritation may occur, although this will be minimized by changing the site of patch application daily. If a subject develops itching or a rash at the patch site, he or she will be advised to use 1% hydrocortisone cream on the affected area. Symptoms associated with nicotine toxicity include lightheadedness, dizziness, nausea, fainting and vomiting. A less likely side effect of nicotine patches is somnambulism.

Potential side effects of Lorcaserin HCl:

Most likely

- Headache
- Dizziness
- Fatigue
- Nausea
- Dry mouth
- Constipation
- Cough
- Back pain

- Low blood sugar (hypoglycemia in participants with diabetes)

Less likely

Lorcaserin HCl may also cause other, potentially serious side effects, including:

- Serotonin Syndrome or Neuroleptic Malignant Syndrome (NMS)-like reactions.
- Valvular heart disease
- Changes in your attention or memory
- Depression or thoughts of suicide
- Low blood sugar (hypoglycemia)
- (For Men) Painful erections (priapism)
- Slow heartbeat
- Decreases in your blood cell count
- Increase in prolactin
- Pulmonary hypertension (high blood pressure in the lungs)

Increases in the proportion of animals with tumors of some tissues, including breast, brain, thyroid gland, liver, skin and nerve sheath, were found in rats, but not mice, given lorcaserin HCl for 2 years at doses which produced blood levels higher than in humans. The relevance of tumors in rats to humans is unknown.

Subjects will be monitored throughout the duration of the study for side effects and severe adverse effects (SAEs). They will be instructed to report any side effects to the study technicians, who will communicate these reports immediately to the medical staff. The most appropriate course of action will be determined, which may include options for dose reduction or termination of treatment. Participants will be reminded that they have the option to withdraw from the study at any time. Subjects will also be given the 24 hour emergency contact numbers in the event that side effects or adverse events occur between sessions. SAEs will be reported to the IRB and will be monitored until resolution or stabilization.

Needle stick / Blood drawing: The risks associated with venipuncture are minimal, and include momentary discomfort and/or bruising. Infection, excess bleeding, clotting, and fainting are also possible, although unlikely.

SERIOUS ADVERSE EVENT REPORTING PLAN

The Principal Investigator will report all serious adverse events relating to the study in an expedited manner to the Duke University Health System (DUHS) Institutional Review Board (IRB) office, and all applicable regulatory authorities in accordance with the Center's standard operating procedures.

COSTS TO PARTICIPANTS

There are no costs to participants for taking part in this study. All the study costs, including any study medications and procedures related directly to the study, will be paid for by the research grant awarded to Duke University. The active lorcaserin and placebo lorcaserin tablets will be supplied by Eisai. The nicotine patch will be purchased from Duke Outpatient Pharmacy.

DATA ANALYSIS & STATISTICAL CONSIDERATIONS

The primary outcome measure will be the time-to-lapse during the laboratory session. McKee et al. (2012) reported an effect size of ~0.8 on this measure, and obtained significant results assessing the therapeutic effects of bupropion and varenicline with n=20 per group. With n=30 per group in the proposed study, and using a one-tailed alpha=0.05 (the hypothesis is one-tailed inasmuch as there would be no interest in pursuing the development of lorcaserin unless an increase in time-to-lapse is demonstrated), we should obtain over 90% power to detect a comparable effect. Secondary outcomes that will be compared between groups include the percent reduction in ad libitum smoking during the first 2 weeks, and withdrawal symptoms reported after 2 hours of smoking abstinence in the laboratory, measures that have been sensitive to treatment in our previous studies of nicotine replacement therapy (NRT) and other treatments. The two treatment groups will be compared on these measures using ANOVA-based statistical methods.

Continuous abstinence from smoking during weeks 7-10 after the quit date will also be tabulated, and 90% confidence intervals will be calculated. Abstinence will also be correlated with the reduction in ad libitum smoking in the first 2 weeks to determine whether smoking reduction may be a useful early marker of therapeutic efficacy. Among smoking-abstinent participants, weight gain relative to baseline will also be assessed, and 90% confidence intervals will be calculated.

Tolerability of treatment will be assessed by tabulating side effect frequencies and degree of adherence to taking medications (percent of total doses taken, assessed by self-report diaries and counts of returned medications at each session).

DATA & SAFETY MONITORING

Description of BP monitoring procedures after study enrollment

After study enrollment, if blood pressure during return sessions is above 160/100, then the following actions will be taken to enhance subject safety:

- If BP >210/100 with symptoms of malignant hypertension: stop experiment interventions and refer to appropriate medical treatment. Resume participation and continue to be monitored if BP is no greater than 140/100.

- If BP > 160/100 for 2 consecutive sessions, then CSC will provide either weekly BP checks or request that the participant have his/her BP checked weekly by PCP, local pharmacy, or home machine and call us with results. The physician assistant will discuss these results with the study physician.
- A blood pressure memo to file form will be completed if BP>160/100 for 3 readings per center approved procedure.

Data Safety Monitoring Plan (DSMP)

We plan to exclude potential participants who take drugs that could interact with lorcaserin by increasing the risk of serotonin syndrome.

To address potential safety issues in addition to collection of the primary study outcomes, severe side effects and adverse events potentially associated with the study will be examined, recorded and then reported to the IRB in a manner consistent with Duke HRPP policies. The principal investigator will be responsible for monitoring data collection and safety of this study.

Data collection for this study will be carried out at the Durham clinical site of the Duke Center for Smoking Cessation (CSC). All members of the study team will complete research integrity (“code of conduct”) and CITI (Collaborative Institutional Training Initiative) Human Research Curriculum and clinical laboratory safety training as required by Duke University Medical Center. All study staff who are involved in data collection, management, and processing will be thoroughly trained following standards of procedures prior to working on this project.

Study staff responsible for data collection will use a checklist for completion for each study visit of each participant. Missing Data Forms, along with explanations should missing data occur, will be completed by the study staff for each study visit.

Microsoft Access will be used for logging subject information (Enrollment Log, Visit Log, etc.). Data will be entered by the study staff. The key study personnel will further examine the computerized data entries and original records for accuracy and completion.

Emergency Unblinding

This is a blinded protocol such that all participants and all study personnel except for the Clinical Research Coordinator and the Research Program Leader are blinded to group allocation. During specific circumstances it will be necessary to unblind other study personnel, such as study team medical personnel. Emergency unblinding will occur under the discretion of the study physician (or one of the study physician assistants) in any situation in which unblinding is deemed necessary to ensure or promote the safety of a study participant. The decision to unblind for safety reasons may occur for a number of reasons and it is not possible to enumerate all potential circumstances. Examples of reasons for unblinding to ensure participant safety include situations in which it is necessary to know which study drugs the subject was taking in order to manage the side effect(s), advise the subject on the risk of future negative drug reactions, uncover potential safety information about the drug, and/or determine whether the adverse event

is study related. In those situations, the Clinical Research Coordinator or Research Program Leader will inform the study physician (or physician assistant handling the event) of that subject's treatment condition. If unblinding occurs, that subject's data will be censored and will not be included in final data analyses.

DATA STORAGE & CONFIDENTIALITY

Any PHI collected prior to documentation of informed consent will be de-identified if the potential subject does not qualify for this study. Please refer to the "Request for Waiver of Documentation of Informed Consent".

